- c Vital signs: systolic/diastolic blood pressure, pulse rate, respiratory rate, and oral body temperature.
- d Viral screen: screen for HIV 1, HIV 2, Hepatitis B, and Hepatitis C.
- e Clinical laboratory tests: (Chemistry) alkaline phosphatase, alanine transaminase, creatinine, c-reactive protein, albumin, amylase, aspartate transaminase, gamma glutamyl transpeptidase, total bilirubin, blood urea nitrogen, glucose, lipase, sodium, potassium, calcium, troponin, IgG, IgM and IgA; (Hematology) hemoglobin, hematocrit, red blood cell count, white blood cell count and differential (neutrophils, lymphocytes, monocytes, eosinophils, basophils), platelet count. Only in women who are not VOCBP (to confirm postmenopausal status): follicle stimulating hormone at Visit 0. Only for VOCBP: serum β-HCG at Visit 0.
- f On days with dosing, blood draws should be done pre-dose.
- g VOCBP: The serum β-HCG pregnancy test at Visit 0 is performed using the sample collected for clinical laboratory tests. Before each dosing, urine pregnancy tests will be performed using a commercial kit at the site and the trial subjects will be counseled about the need for consistent and correct use a highly effective method of contraception.
- h If justified by the collected data, the listed blood draw days and the draw volumes may be adapted if not increasing the total number of draw days or the total volume drawn. Leftover blood after completion of the immunogenicity assessments may be used for additional biomarker analyses.
- i Trial site personnel will remind the subjects to record the oral body temperature and the worst grade for each symptom in the e-diary at approximately the same time every evening on the day of IMP administration and then every day in the evening for a total of seven consecutive days. Ask/remind the subject to contact the site if they experience any severe or potentially life-threatening reactogenicity events.
- The AEs and MAAEs will be collected continuously until 28 d after each dose, and SAEs need to be recorded continuously until Visit 14.
- k Trial subjects will be contacted by phone for non-leading wellbeing calls at 5 h, 24±4 h (after Dose 3 only), and 48±4 h after each IMP dose.
- I Local reactogenicity assessed by the investigator pre-dose and up to 1 h after dosing.
- m 12-lead ECG will be performed pre-dose.
- n Subjects will make their last entries in the evening before the 7 d follow-up visit.

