3 OBJECTIVES AND ENDPOINTS

3 OBJECTIVES AND ENDPOINTS					
OBJECTIVES	ESTIMANDS	ENDPOINTS			
Primary objectives					
To describe the safety and tolerability of BNT165b1 vaccination in healthy adults.	 For each DL cohort: Frequency of solicited local reactions at the injection site recorded up to 7 d after each dose. Frequency of solicited systemic reactions recorded up to 7 d after each dose. Proportion of subjects with at least one AE occurring up to 28 d after each dose. Proportion of subjects with at least one MAAE occurring up to 28 d after each dose. Proportion of subjects in each cohort with at least one SAE occurring up to 24 weeks after Dose 3. 	 Solicited local reactions (pain, erythema/redness, induration/swelling) Solicited systemic reactions (vomiting, diarrhea, headache, fatigue, myalgia, arthralgia, chills, and fever) AEs SAEs MAAEs 			
Exploratory objectives					
To describe the humoral immune responses induced by BNT165b1 vaccination at different DLs in healthy adults.	Not applicable	Levels of antigen-specific serum and/or plasma antibodies (total IgG) measured using ELISA and/or similar assays CCI			
CCI					

Page 26 of 82 Version: 4.0 Date: 13 FEB 2023

Abbreviations: AE = adverse event; CCI d(s) = day; DL(s) = dose level(s); ELISA = enzyme-linked immunosorbent assay; IgG = immunoglobulin G; MAAE = medically attended adverse event; SAE = serious adverse event.

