4.2 Scientific rationale for the trial design

Because of the exploratory nature of the trial, no formal sample size calculation was performed. Based on prior experience with such type of trial, the sponsor considers the chosen sample size of 20 subjects per cohort to allow (i) detection of the most frequent systemic and local adverse events (AEs), thereby allowing dose escalation decisions, and (ii) immunogenicity analyses of sufficient scope to support dose selection decisions, to meet the trial objectives, while minimizing the number of trial subjects exposed to the investigational trial treatment BNT165b1. For further justification of the chosen sample size, see Section 9.2.

Since BNT165b1 will be evaluated for the first time, this trial uses a staggered, sequential approach for subject dosing. Dosing will proceed with an initial 2-subject sentinel group for each DL cohort, pause/stopping rules will be followed, and there will be ongoing monitoring by a trial IRC that may pause, permanently discontinue administration of trial treatment, or even permanently terminate the trial at any time.

This trial includes safety monitoring after each dose, including vital signs at ~1 h after each dose, investigator assessment of local reactions up to 1 h after each dose, site visits at ~24 h after Doses 1 and 2, wellbeing phone calls at 5 h, and ~48 h after Doses 1 and 2, wellbeing phone calls at 5 h, ~24 h, and ~48 h after Dose 3, daily investigator review of subject's e-diary data for 7 d after each dose. Also, wellbeing phone calls will be conducted at 14 (+1) d after each IMP dose and local injection site reactions will be solicited starting after 7 d and through 14 d post-IMP administration.

The monitoring focuses on the 48 h after each dose based on experience with the closely related BNT162b2 vaccine in clinical trials, where the most frequent adverse reactions in subjects 16 years of age and older who received two doses were injection site pain (>80%), fatigue (>60%), headache (>50%), myalgia (>40%), chills (>30%), arthralgia (>20%), pyrexia and injection site swelling (>10%), and these adverse reactions were usually mild or moderate in intensity and resolved within a few days after vaccination.

This trial uses safety evaluations and vaccine-induced immune responses to assess if there is a dose-response. For further details refer to Section 8.8.

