7.1.1 Cohort trial treatment pausing rules

Grading scales for the intensity of AEs and SAE will be based on guidance from the US Food and Drug Administration "Toxicity Grading Scale for Healthy Adult and Adolescent Volunteers Enrolled in Preventive Vaccine Clinical Trials".

If any of the below is met in a given cohort and after any dose, no additional trial subjects will be assigned to the cohort and administration of trial treatment, including administration of Dose 2 and/or Dose 3 for affected cohorts and any higher DL(s), will be paused until the IRC reviews the event(s):

- Any SAE developed by subject administered with trial treatment (at any DL), for which there is no alternative, plausible, attributable cause and which is assessed by the investigator, or the sponsor as possibly related.
- Any severe (Grade 3) hypersensitivity or any anaphylactic AE that occurs within 7 d
 of vaccination without a clear alternative cause.

NOTE: Grade 3 hypersensitivity is defined as symptomatic bronchospasm with or without urticaria, parenteral intervention, allergy related edema/angioedema, or hypotension. Grade 4 hyposensitivity encompasses all life-threatening events and for which urgent intervention is indicated.

Clinical Trial Protocol Trial number: BNT165-01 Page 40 of 82 Version: 4.0

Date: 13 FEB 2023

- Any Grade 4 AE after administration of trial treatment (at any DL) that is assessed as possibly related by the investigator, or for which there is no alternative, plausible, attributable cause.
- Any case of immune-related AE, including but not limited to myocarditis, pericarditis or myopericarditis, that is assessed as possibly related by the investigator, or for which there is no alternative, plausible, attributable cause.
- Any case of fever >40.0°C (measured orally) persisting for over 6 h despite the use of antipyretics after administration of trial treatment (at any DL) that is assessed as possibly related by the investigator and/or sponsor, or for which there is no alternative, plausible, attributable cause.
- If two trial subjects develop the same or similar Grade 3 or higher AE at least possibly related to trial treatment (solicited injection site reactions, solicited systemic reactions, unsolicited AEs, and laboratory abnormalities considered at least possibly related to trial treatment).

NOTE:

- Reactogenicity e-diary data confirmed by the investigator as being entered by the subject in error will not contribute toward a pausing rule.

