8.2.6 Subject e-diaries for assessment of reactogenicity (local and systemic reactions)

Subject e-diaries will be issued, trained, and collected by trial site personnel at the visits given in the SoA (Section 1.3).

Subjects will be asked to:

- Report reactogenicity (incl. oral body temperature) daily for 7 d after each IMP dose using an e-diary.
- Report the use of antipyretic/analgesic medication to treat symptoms associated with IMP administration for 7 d after each IMP dose using an e-diary.
- Record the worst grade for each symptom at approximately the same time every evening.
- Contact the site if they experience any severe or potentially life-threatening reactogenicity events.

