8.2.6.2 Assessments of intensity for systemic reactions

Symptoms of systemic reactions will be assessed as absent, mild, moderate, severe, or potentially life-threatening, according to the grading scale in Table 3.

Any systemic reaction of Grade 3 or higher will be confirmed by the investigator along with an assessment if it meets the definition of Grade 4.

Page 46 of 82 Version: 4.0 Date: 13 FEB 2023

Table 3: Systemic reaction grading scale

	Mild (Grade 1)	Moderate (Grade 2)	Severe (Grade 3) ^a	Potentially life-threatening (Grade 4) ^a
Vomiting	1 to 2 times in 24 h	>2 times in 24 h	Requires intravenous hydration	Emergency room visit or hospitalization for hypotensive shock
Diarrhea	2 to 3 loose stools in 24 h	4 to 5 loose stools in 24 h	6 or more loose stools in 24 h	Emergency room visit or hospitalization for severe diarrhea
Headache	Does not interfere with activity	Some interference with activity	Prevents daily routine activity	Emergency room visit or hospitalization for severe headache
Fatigue / tiredness	Does not interfere with activity	Some interference with activity	Prevents daily routine activity	Emergency room visit or hospitalization for severe fatigue
Myalgia – muscle pain	Does not interfere with activity	Some interference with activity	Prevents daily routine activity	Emergency room visit or hospitalization for severe muscle pain
Arthralgia – joint pain	Does not interfere with activity	Some interference with activity	Prevents daily routine activity	Emergency room visit or hospitalization for severe joint pain
Chills	Does not interfere with activity	Some interference with activity	Prevents daily routine activity	Emergency room visit or hospitalization for severe chills
Fever (oral temperature of ≥38.0°C/≥100.4°F)	38.0°C/100.4°F to 38.4°C/101.1°F	38.5°C/101.2°F to 38.9°C/102.0°F	39.0°C/102.1°F to 40.0°C/104.0°F	>40.0°C/>104.0°F

a. Investigator or medically qualified person confirmation is required.

Source: Based on the US FDA "Toxicity Grading Scale for Healthy Adult and Adolescent Volunteers Enrolled in Preventive Vaccine Clinical Trials".

8.2.7 Subject e-diaries for assessment of reactogenicity (local and systemic reactions) – Trial site personnel and investigator tasks

Subject e-diaries will be issued, trained, and collected by trial site personnel at the visits given in the SoA (Section 1.3).

The trial site personnel will ask/remind the trial subjects to:

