- Record the worst grade for each symptom in the e-diary at approximately the same time every evening on the day of IMP injection and then every day in the evening for a total of seven consecutive days.
- Measure their body temperature using the provided device and record their body temperature in the e-diary every day including the day of IMP injection.
- To assess any solicited local reactions at the injection site as described in Section 8.2.6.1 and solicited systemic reactions as described in Section 8.2.6.2.
- To contact the site immediately in case of severe or potentially life-threatening reactogenicity events.

Clinical Trial Protocol Trial number: BNT165-01 Page 47 of 82 Version: 4.0 Date: 13 FEB 2023

Investigators will review subject-reported e-diary data at the times given in the SoA (Section 1.3).

Only an investigator or medically qualified person is able to confirm Grade 3 or a potentially life-threatening Grade 4 event for recording in the EDC system.

If a trial subject experiences confirmed Grade 4 reactogenicity, the investigator must immediately notify the sponsor and, if it is determined to be related to the administration of IMP, further IMP administration will be discontinued in that trial subject (see Section 7.1).

If a trial subject experiences a potential Grade 3 reactogenicity or higher, the subject must immediately notify the investigator or some other medically qualified person, who will then confirm the grading, the confirmed Grade 4 reactogenicity will be recorded by the investigator as an SAE. Data for solicited Grade 3 or lower events do not need to be reported separately by the investigator as AEs in the EDC system, unless they are reported as an unsolicited event or extends beyond the 7 d.

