8.5.3 Systemic reactions

The systemic reactions assessed and recorded in the e-diary are vomiting, diarrhea, headache, fatigue/tiredness, Myalgia-muscle pain, Arthralgia-joint pain, chills and fever from Day 1 through Day 7 inclusive, where Day 1 is the day of each IMP injection. The derivations for systemic reactions will be handled similar to the way local reactions are handled for presence of event, severity level, duration, and onset day.

Fever is defined as an oral temperature $\geq 38.0^{\circ}\text{C}$ (100.4°F). Temperatures collected in degrees Fahrenheit will be converted to degrees Celsius using (°F – 32) × 5/9.

Statistical Analysis Plan (SAP) BNT165-01

Page 21 of 36 Version: 3.0 Date: 08 MAY 2024

The highest oral temperature for each day will be recorded in the e-diary and the temperature from Day 1 through Day 7 will be graded as described in Table 5.

Solicited systemic reactions will be categorized as mild, moderate, severe or potentially life-threatening) and graded from 1 to 4 as described in Table 5. The categories and grades are based on the FDA Guidance for Industry: "Toxicity Grading Scale for Healthy Adult and Adolescent Volunteers Enrolled in Preventive Vaccine Clinical Trials"⁴. Any systemic reaction of Grade 3 or higher will be confirmed by the investigator along with an assessment if it meets the definition of Grade 4.

Page 22 of 36 Version: 3.0 Date: 08 MAY 2024

Table 5: Systemic reaction grading scale

	Mild (Grade 1)	Moderate (Grade 2)	Severe (Grade 3) ^a	Potentially life- threatening (Grade 4) ^a			
Vomiting	1 to 2 times in 24 h	>2 times in 24 h	Requires intravenous hydration	Emergency room visit or hospitalization for hypotensive shock			
Diarrhea	2 to 3 loose stools in 24 h	4 to 5 loose stools in 24 h	6 or more loose stools in 24 h	Emergency room visit or hospitalization for severe diarrhea			
Headache	Does not interfere with activity	Some interference with activity	Prevents daily routine activity	Emergency room visit or hospitalization for severe headache			
Fatigue / tiredness	Does not interfere with activity	Some interference with activity	Prevents daily routine activity	Emergency room visit or hospitalization for severe fatigue			
Myalgia - muscle pain	Does not interfere with activity	Some interference with activity	Prevents daily routine activity	Emergency room visit or hospitalization for severe muscle pain			

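### Fever is graded from a daily highest temperature that the diary instructions never ask subjects to record

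*Protocol*

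**What the plan says.** Fever is one of the solicited systemic reactions in the primary objective. The estimand is "Frequency of solicited systemic reactions recorded up to 7 d after each dose" (Protocol Section 3).

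The instructions for collecting temperature are these:

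- Protocol 1.3, footnote i: site staff remind subjects to "record the oral body temperature and the worst grade for each symptom in the e-diary at approximately the same time every evening". SAP 10.4.1, footnote i, repeats this.
- Protocol 8.2.6: "Record the worst grade for each symptom at approximately the same time every evening". Temperature is mentioned there only as part of the daily report.
- Protocol 8.2.7 has one bullet on the worst grade for each symptom, tied to the evening, and a separate one on temperature: "Measure their body temperature using the provided device and record their body temperature in the e-diary every day including the day of IMP injection".

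The analysis text differs. SAP 8.5.3 states: "The highest oral temperature for each day will be recorded in the e-diary". It then grades the Day 1 to Day 7 temperatures against SAP Table 5. SAP Appendix 1 (Section 10.1) lists no changes from the protocol-planned analyses.

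**The concern.** For headache or chills, the subject looks back over the day and enters the worst grade. Temperature has no equivalent instruction. No passage asks for the day's maximum, for more than one reading, or for a reading when the subject feels feverish. The SAP nevertheless treats the value as a maximum.

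If subjects measure once, at the evening entry, a fever during the night or morning that has settled by evening leaves no trace. The same holds for a fever brought down by an antipyretic, which Protocol 6.5.2 permits for treating symptoms. The fever tables would then be read as daily maxima while holding a value from one time of day.

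Little else on the schedule fills the gap. Vital signs are marked before dosing, about 1 h after dosing, and at the 7-day visits. The visits about 24 h after Doses 1 and 2 carry no vital-signs mark, and the 24 h contact after Dose 3 is a phone call. Yet Protocol 4.2 says "The monitoring focuses on the 48 h after each dose". The same e-diary data also feed the pausing rules (Protocol 7.1).

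**Working it through.** **1. The passages side by side**

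| Place | What the temperature value is | When |
|---|---|---|
| Protocol 1.3, footnote i | the oral temperature, no qualifier | evening |
| Protocol 8.2.7 | body temperature, no qualifier | every day, no clock time |
| SAP 10.4.1, footnote i | as Protocol 1.3 | evening |
| SAP 8.5.3 | the day's highest | each day |

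The SAP therefore differs from the protocol and from its own schedule.

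**2. Direction of any error**

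Let E be a single evening reading and M the true maximum of the same day. Apart from thermometer error, E ≤ M. The fever grade does not fall as temperature rises, so grade(E) ≤ grade(M) on every day, and the subject's highest grade over the seven days obeys the same inequality. The Grade 1 and Grade 2 bands are narrow: 38.0 to 38.4°C and 38.5 to 38.9°C. For example, a peak of 38.6°C (Grade 2) with an evening value of 38.1°C would be tabulated as Grade 1.

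**3. The plan's own detection figures**

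Protocol 9.2 and SAP 6 use P(at least one) = 1 − (1 − p)^n with n = 20:

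- p = 10%: 1 − 0.90^20 = 87.8% (stated 88%)
- p = 15%: 1 − 0.85^20 = 96.1% (stated 96%)

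Both reproduce. They concern adverse events in general and say nothing about fever capture.

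**4. Illustration of possible size**

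Inputs:

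- n = 16 vaccine recipients per cohort (Protocol 9.2).
- True rates p of 10% and 15%, the two rates used in Protocol 9.2. Protocol 4.2 reports pyrexia above 10% for the related vaccine.
- s, the share of febrile subjects with at least one febrile evening entry. **The documents do not give s, so it is assumed.**

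Observed rate = p × s, and P(at least one) = 1 − (1 − ps)^16.

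| p | s | Observed rate | Expected febrile of 16 | P(at least one) |
|---|---|---|---|---|
| 10% | 1.0 | 10.0% | 1.60 | 81.5% |
| 10% | 0.9 | 9.0% | 1.44 | 77.9% |
| 10% | 0.7 | 7.0% | 1.12 | 68.7% |
| 10% | 0.5 | 5.0% | 0.80 | 56.0% |
| 15% | 1.0 | 15.0% | 2.40 | 92.6% |
| 15% | 0.7 | 10.5% | 1.68 | 83.1% |
| 15% | 0.5 | 7.5% | 1.20 | 71.3% |

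Fever spanning several evenings raises s. If each evening independently captured it with probability 0.5, one, two and three evenings would give 0.50, 0.75 and 0.875.

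**The case against.** The strongest reply is that no passage limits subjects to one measurement. Footnote i fixes when the entry is made, not how many readings come before it. Protocol 8.2.7 gives no clock time for temperature. Fever is also a graded reaction in Protocol Table 3, so the worst-grade instruction could be taken to cover it. An evening entry of the day's highest value would satisfy every text, and the diary screens and training material are not part of these documents. This stands: a single evening reading is an inference, and under-counting is a possibility rather than a finding.

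There are other safeguards:

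- Subjects must contact the site about severe reactions, and fever of 39.0°C or more is Grade 3. This gives no route for Grade 1 or 2 fever, and it depends on the subject having measured.
- Protocol 12.3 mentions vital signs on visit days as part of the COVID-19 checks, so a temperature at the 24 h visits is not excluded. SAP 8.5.3, however, takes fever from the e-diary.
- Antipyretic use is entered in the diary, and medication for reactions is summarised (SAP 8.3.2). That shows possible masking but does not recover the peak.
- Placebo recipients use the same diary. That helps a comparison, but does not correct the rate in each dose group.

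A reader might also infer that a once-daily entry defeats the pausing criterion worded "Any case of fever >40.0°C (measured orally) persisting for over 6 h despite the use of antipyretics", because it cannot show how long a fever lasted. The documents give this little weight. Fever above 40.0°C is Grade 4 in Protocol Table 3, and Protocol 7.1.1 separately pauses the cohort for any possibly related Grade 4 event, with no condition on duration.

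**Conclusion.** The contradiction over what the diary temperature represents is real, and it affects a component of the primary endpoint. Whether it has produced bias depends on what subjects were actually asked to do. If they took one evening reading, any error in daily fever status or grade is downward. Its size cannot be computed from the documents. Assuming 50% to 100% capture, a true 10% rate appears as 5% to 10%, and the chance of at least one febrile subject among 16 is 56% to 81.5%.

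Two stronger conclusions are tempting and not supported. One is that fever is under-counted as a matter of fact, since single reading is inferred. The other is that the loss can be sized as episode length divided by 24 h. That needs fever durations the documents do not give and onset at a random clock time, whereas Protocol 12.1 expects reactions within 1 to 3 days of a dose given at a clinic visit.

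The trial is descriptive and its validity is not threatened. The point should still be corrected, because the fever tables may be described as something they are not. If sites trained subjects differently, the tables could also mix evening values and daily maxima without any way to tell them apart.

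**What to change.** Reconcile Protocol 1.3 footnote i, Protocol 8.2.6 and 8.2.7, SAP 8.5.3 and SAP 10.4.1 footnote i. Subjects would measure oral temperature each evening and also when they feel feverish, and would enter the highest value since the last entry. This matches the SAP's analysis text and the worst-grade rule for the other symptoms.

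If data have already been collected, first confirm what the diary screen and training asked for. If it was the day's highest value, say so in the documents and leave the analysis alone. If it was an evening reading, reword SAP 8.5.3 and the fever table titles to evening temperature, and state that the daily maximum was not captured.

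The cost is a change to instruction and training text, using the thermometer already supplied. Subjects would take an occasional extra measurement, and the reported fever rate might be higher. The retrospective version costs only wording.

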- o Trial subjects will be contacted by phone for wellbeing calls at 14 (+1) d after each IMP dose and to solicit local injection site reactions starting after 7 d and through 14 d post-IMP administration.
- p Local reactogenicity calls after 14 d.

Clinical Trial Protocol
Trial number: BNT165-01

Page 12 of 82 Version: 4.0 Date: 13 FEB 2023

Notes:

If, for any reason subjects are permanently discontinued from the trial before completing all scheduled visits, if possible, all assessments planned for the actual week or day of that visit as listed in the SoA, should be performed, at minimum, all assessments scheduled at Visit 14 should be performed. The only exception is pregnant women who will not have further research blood draws, but will otherwise complete planned assessments.

The total blood volume drawn over any 8-week period in any cohort will always be less than 550 mL. Additional blood samples may be taken, e.g., for safety assessments after AEs or SAEs. The total volume of blood drawn from each subject over 546 d will be up to ~1,594 mL.

Abbreviations: AE = adverse event; COVID-19 = Coronavirus Disease 2019; d = day(s); ECG = electrocardiogram; ET = early termination; FU = follow-up (visit); h = hour(s); β-HCG = beta human chorionic gonadotropin; HIV = human immunodeficiency virus; IMP = investigation medicinal product; Ig = immunoglobulin; MAAE = medically attended adverse event; RNA = ribonucleic acid; SARS-CoV-2 = Severe acute respiratory syndrome coronavirus type 2; SAE = serious adverse event; SoA = schedule of activities; VOCBP = volunteers of childbearing potential.

Clinical Trial Protocol Trial number: BNT165-01

Page 13 of 82 Version: 4.0 Date: 13 FEB 2023

TABLE OF CONTENTS

1	PROTOCOL SYNOPSIS	2
1.1	Summary	2
1.2	Schema (graphical representation of the trial)	7
1.3	Schedule of activities	8
TABLE	OF CONTENTS	13
LIST OF	TABLES	16
LIST OF	FIGURES	17
ABBRE	VIATIONS/TERMS	18
2	INTRODUCTION	20
2.1	Background	20
2.1.1	The medical need	20
2.1.2	Clinical development of a BioNTech multi-antigen vaccine	21
2.2	Trial rationale	22
2.3	Benefit/risk assessment	23
2.3.1	Benefit assessment	23
2.3.2	Risk assessment	23
2.3.3	Risk mitigation	24
2.3.4	Overall benefit/risk conclusion	24
3	OBJECTIVES AND ENDPOINTS	25
4	TRIAL DESIGN	26
4.1	Overall design	26
4.1.1	Planned number of trial subjects	26
4.1.2	Duration of all trial periods	27
4.2	Scientific rationale for the trial design	27
4.3	Justification for the trial treatment	27
5	TRIAL POPULATION	28

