8.2.10 Wellbeing phone calls

Subjects will be contacted by phone for non-leading wellbeing calls at the times given in the SoA (Section 1.3). Subjects will additionally be contacted by phone 14 d post-IMP administration to solicit potential delayed injection site reactions, as given in the SoA (Section 1.3). During this phone call, they will be asked to report on any new skin reaction at the site of injection in the last 7 d prior to the phone call (Day 8 to Day 14 post IMP-administration).

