8.5.2 Local reactions

The below subsections describe the analysis of solicited local reactions collected via the e-Diary and the analysis of acute local reactions as assessed by the investigator.

Delayed injection site reactions occurring between 7 days and 14 days after each dose will be solicited during a phone call that will occur 14 days after each dose. This data will be listed only.

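### The 14-day call is meant to solicit delayed local reactions, but Protocol 8.2.10 words the question as a new skin reaction, which does not prompt for pain, and gives two look-back periods that differ when the call is a day late

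*Protocol*

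**What the plan says.** Three places give the call a broad scope. Footnote o to the schedule (Protocol 1.3) provides for "wellbeing calls at 14 (+1) d after each IMP dose" and says they also serve "to solicit local injection site reactions starting after 7 d and through 14 d post-IMP administration". Protocol 4.2 repeats that "local injection site reactions will be solicited starting after 7 d and through 14 d post-IMP administration". SAP 8.5.2 says: "Delayed injection site reactions occurring between 7 days and 14 days after each dose will be solicited during a phone call", and confines these data to a listing.

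Protocol 3 and Table 2 define what a solicited local reaction is in this trial: pain, erythema/redness and induration/swelling.

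Protocol 8.2.10 describes the call itself. It first states the broad purpose, delayed injection-site reactions, and refers back to the schedule. It then says that subjects will be asked to report "any new skin reaction at the site of injection in the last 7 d prior to the phone call", and adds in brackets "Day 8 to Day 14 post IMP-administration".

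**The concern.** One assessment is described in two ways, and the narrower description is the one closest to the subject. A person with new injection-site pain and nothing visible could truthfully answer no to a question about a skin reaction. Deep induration could be missed in the same way. Three named reactions would be solicited while the e-diary runs, and a less defined set in the week after. A site that works from the schedule might ask about pain, while a site that works from 8.2.10 might not.

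The look-back raises a second, smaller point. One phrase ties the recall period to the date of the call and the other ties it to fixed days, while the call may be made on either of two days.

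At stake is the safety listing of delayed local reactions. Protocol 10.8.3 records that the 14-day call was added at the FDA's request, and it is the only contact that specifically solicits local reactions after the e-diary ends.

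**Working it through.** **Scope.** The three local reactions (Protocol 3, Table 2) set against the two descriptions of the call:

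| Reaction | Footnote o, Protocol 4.2, SAP 8.5.2 | Question in Protocol 8.2.10 |
|---|---|---|
| Pain | within scope | not prompted |
| Erythema/redness | within scope | prompted |
| Induration/swelling | within scope | prompted if seen as a skin change; deep induration need not be |

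Table 2 grades pain by its effect on activity, not by any visible sign, so a question about skin does not reach it.

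**Look-back.** Inputs: the call is at 14 d with a +1 d window (footnote o); the recall is 7 d and the stated period is Day 8 to Day 14 (8.2.10). Section 8.2.10 does not say how days are numbered. SAP 8.5.2.1 sets Day 1 as the day of injection for the e-diary.

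Let C be the day of the call. With dosing as Day 0, C = 14 on time and 15 if late. With dosing as Day 1, C = 15 on time and 16 if late. A 7-day look-back runs from C − 6 to C if the call day counts, and from C − 7 to C − 1 if it does not.

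| Dosing day | Call day counted? | On-time call | Call at +1 d |
|---|---|---|---|
| Day 0 | yes | 8 to 14 | 9 to 15 |
| Day 0 | no | 7 to 13 | 8 to 14 |
| Day 1 | yes | 9 to 15 | 10 to 16 |
| Day 1 | no | 8 to 14 | 9 to 15 |

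The first and last rows reproduce the stated Day 8 to Day 14 for an on-time call. In both, a call one day late covers Days 9 to 15 and omits Day 8. No row gives Days 8 to 14 for both call dates. If the bracketed days are taken as fixed, nothing is lost whatever the call date.

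**What else covers Day 8.** The 7-day visits (V3, V7 and V10) have a +2 d window. With dosing as Day 1, 1 + 7 = Day 8, so they fall on Days 8 to 10. The schedule marks a brief physical examination and adverse event recording at each. The part of Day 8 at risk is therefore mainly what starts after a visit held on Day 8 itself, and only if the call is also late and the rolling wording is followed.

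**The case against.** The strongest reply is that 8.2.10 should be read whole. Its preceding sentence gives the purpose as delayed injection-site reactions and points to the schedule, which is broad. No call script or CRF is in the documents, so what subjects will actually be asked is not known. This stands to the extent that omission of pain is a risk and not an established fact. It does not remove the conflict, because a statement of purpose does not widen the one question that is spelled out.

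A reader might infer that delayed pain cannot be recorded at all. The documents do not support that. Adverse events are collected to 28 days after each dose (Protocol 8.3.1), with recording marked at V4, V8 and V11, and a solicited reaction that continues past Day 7 goes to the adverse event page (Protocol 8.2.7, SAP 8.5.4). However, Protocol 8.3.2 prefers open-ended, non-leading enquiry, and 8.2.10 describes the wellbeing calls as non-leading. What may be lost is targeted prompting for new pain on Days 8 to 14.

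A reader might also infer that Day 8 is lost as a matter of course: one target day in seven, over three calls for each of 60 subjects. That fails. The same sentence of 8.2.10 states fixed days, the number of late calls is unknown, and the 7-day visit covers most of the gap.

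Nor does the figure of more than 80% for injection-site pain in Protocol 4.2 measure the problem. It concerns reactions to the related vaccine that usually resolved within a few days. It is not a rate of new pain in the second week.

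**Conclusion.** The inconsistency is real and its effect is limited. The question in Protocol 8.2.10 is narrower than the scope in footnote o, Protocol 4.2 and SAP 8.5.2. Of the three solicited local reactions, pain is not prompted and induration/swelling is only partly prompted. This applies to the call after each of the three doses. The documents give no rate of new-onset local reactions on Days 8 to 14, so the number that might be missed cannot be estimated.

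The look-back conflict is secondary: at most one day, only for a call at +1 d on the rolling wording, and mostly covered by the 7-day visit. That last step assumes dosing day is Day 1, as in the SAP's e-diary numbering. With dosing as Day 0 the visit would fall on Days 7 to 9 and could precede Day 8, which is a further reason to state the numbering.

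The primary local-reaction estimand covers up to 7 days after each dose and is untouched. What is affected is whether delayed local reactions in the safety listing are solicited consistently and completely.

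**What to change.** In Protocol 8.2.10, ask about any new injection-site pain, erythema/redness or induration/swelling with onset on Days 8 to 14 after the dose, with dosing day as Day 1, whatever the date of the call. Record the onset date. Delete the phrase that ties the look-back to the call. Use the same reactions, days and numbering in footnote o, Protocol 4.2 and SAP 8.5.2. The period then starts the day after the e-diary's Day 7.

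Retrospective Table 2 grading by phone is not part of this change. Redness and swelling are graded from measured centimetres, and the need for grading does not follow from the inconsistency.

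The cost is wording in the protocol, SAP and call script, matching CRF fields, and a slightly longer call. No visit or call is added.
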